### 13.4 Analysis of Secondary Endpoints

T-test or a linear regression model (with no covariates other than study arm).

Adverse events will be tabulated by treatment group and will include the number of patients for whom the event occurred, the rate of occurrence, and the severity and relationship to study drug.

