	

• entropion repair;

• external dacryocystorhinostomy;

• external levator resection;

• eyelid lesion removal and/or biopsy;

• eyelid reconstruction and defect repair including after Mohs surgery;

• fat pad excision (upper and lower lids);

• gold or platinum weight implantation;

• internal levator resection;

• lateral tarsal strip;

• orbital fracture repair requiring periorbital incisions;

• orbitotomy requiring periorbital incisions;

• tarsorrhaphy;

• wedge excision.

• Patients undergoing repeat procedures will also be included.

 
Exclusion Criteria:
 

• Patients aged younger than 18 years old who are undergoing the above eyelid procedures in an office, ambulatory care centers, operating rooms;

• patients undergoing chalazion removal;

• patients who have had previous wound infections at the site of the procedure;

• patients with oral or IV antibiotic use within 10 days prior to procedure;

• patients requiring IV antibiotics during the procedure;

• patients with grossly contaminated or inflamed wounds;

• patients with human or animal bites,

• patients with wounds resulting from trauma

• patients allergic to all study drug options.

--	--

TEST PRODUCT, DOSE, AND ROUTE OF ADMINISTRATION	Topical Ophthalmic Antibiotic Ointment (e.g. poly-bacitracin, bacitracin). Apply a thin ribbon to surgical wounds 4 times a day (while awake) for 7 days.
CONTROL PRODUCT, DOSE AND ROUTE OF ADMINISTRATION	Artificial Tear Ointment (e.g. Refresh PM). Apply a thin ribbon to surgical wounds 4 times a day (while awake) for 7 days.
DURATION OF SUBJECT PARTICIPATION AND DURATION OF STUDY	Subjects will be on study for up to 14 days. Screening: During pre-operative assessment. Treatment Duration: 7 days Follow-up: 7-14 days The total duration of the study is expected to be 2 years with ongoing subject recruitment. Each subject will have a final follow-up at post-operative week 1 and/or post-operative week 2 unless a post-operative infection occurs. In the event of a post-operative infection, final follow-up will occur upon infection resolution.
CONCOMITANT MEDICATIONS	Allowed: All non-antimicrobial medications.  Prohibited: Antibiotics taken by IV or by mouth.

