## 3 STUDY DESIGN

### 3.1 Study Overview

This is a single center, placebo-controlled, randomized trial. 400 subjects are planned. Subjects will be randomly assigned to a study drug or to a placebo. Each subject will apply a single dose of topical study drug or placebo four times daily to their surgical wounds over the course of one week.

Screening data will be reviewed to determine subject eligibility. Subjects who meet all inclusion criteria and none of the exclusion criteria will be entered into the study.

The following treatment regimens will be used:

- Experimental treatment: topical ophthalmic antibiotic ointment (e.g. erythromycin, bacitracin or polybac)
- Placebo: artificial tear ointment (e.g. Refresh PM)

Total duration of subject participation will be from the time of approval for eyelid surgery to post-operative visit #1 (either one or two weeks after surgery). Total duration of the study is expected to be 2 years.

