## 9.3 Visit 3 (Only if surgical site infection present at Visit 2.)

1. Record any Adverse Experiences and/or Review subject diary for adverse experiences and dosing compliance.
2. Record changes to concomitant medications.
3. Perform abbreviated eye examination.
4. Note duration of treatment and if infection resolved.

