### 10.2.1 Serious Adverse Experience Reporting

Study sites will document all SAEs that occur (whether or not related to study drug) per [UCSF CHR Guidelines](#). The collection period for all SAEs will begin after informed consent is obtained and end after procedures for the final study visit have been completed.

In accordance with the standard operating procedures and policies of the local Institutional Review Board (IRB)/Independent Ethics Committee (IEC), the site investigator will report SAEs to the IRB/IEC.

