4.3 Safety outcomes

Adverse events

Adverse events are reported at each clinic visit.

Concomitant medications

Usage of medications during study period will be recorded.

5. Populations and subgroups to be analyzed

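### The general adverse event table by arm mixes unequal collection windows: infected patients are followed longer, so in expectation the arm with more infections gains adverse events

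*Protocol*

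**What the plan says.** **Length of follow-up.** The Protocol Synopsis states: "Each subject will have a final follow-up at post-operative week 1 and/or post-operative week 2 unless a post-operative infection occurs". It continues: "In the event of a post-operative infection, final follow-up will occur upon infection resolution". No upper time limit is given. Protocol 3.1 ends participation at the first post-operative visit, one or two weeks after surgery.

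**The extra visit.** Protocol 9.3 is headed "Visit 3 (Only if surgical site infection present at Visit 2". Its first step is "Record any Adverse Experiences and/or Review subject diary for adverse experiences and dosing compliance".

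**Collection of adverse events.** Protocol 10.1 has the investigator ask about adverse events at every visit. Protocol 10.2.1 has serious event collection "end after procedures for the final study visit have been completed", that is, at each patient's own last visit. SAP 4.3 states: "Adverse events are reported at each clinic visit".

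**Analysis.** Protocol 13.4: "Adverse events will be tabulated by treatment group and will include the number of patients for whom the event occurred, the rate of occurrence", followed by severity and relationship to study drug. Neither document gives this table a cut-off date, a person-time denominator or a separate presentation of Visit 3 events.

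**Timing of endpoints.** Protocol 8 places the primary and secondary endpoints at Visit 2. Protocol 9.2 (item 5) checks every patient there for allergy to either ointment. SAP 2 places outcome assessment at the first post-operative visit.

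**The concern.** How long a patient is observed for adverse events depends on the primary outcome. A patient found infected at Visit 2 gets a further visit at which events are sought, after treatment for infection has started (Protocol 9.2, item 7). A patient without infection generally does not. If infections are commoner without antibiotic, which is the scenario behind the SAP's power statement, more control patients have the longer window. The control column of the adverse event table then fills up for a reason unrelated to the ointment.

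This matters because antibiotic-related complications are part of the trial's rationale (Protocol 1) and the type and frequency of reactions is a secondary objective (Protocol 2.2). A by-arm table whose columns cover different amounts of follow-up is a poor basis for comparing harm. SAP 2 and SAP 4.3 also leave it unclear whether events after the first post-operative visit belong in the table.

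**Working it through.** **Plan's own figures.** The documents give no adverse event rate and no time to infection resolution, so there is no stated figure on this point to reproduce. The infection scenario used below is the one behind the 87% power in SAP 2.1. That figure reproduces: exact power of Fisher's test, two-sided 0.05, 200 v 200, 0.2% v 5%, is 87.1%.

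**Inputs from the documents**
- 200 patients per arm (Protocol 13.6).
- Infection rate with antibiotic 0.2% (SAP 2.1; Protocol 1, for blepharoplasty).
- Infection rate without antibiotic 0.7% (Protocol 1, dermatological procedures; SAP 2.1 table), 2% (SAP 2.1 table) or 5% (SAP 2.1, maximum acceptable).
- Visit 2 at day t = 7 or 14 (Protocol 3.1).

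**Assumptions**
- Adverse event risk by Visit 2, b = 5% to 20%, equal in both arms.
- x = 7 to 28 days from Visit 2 to resolution.
- A constant hazard, equal in both arms.

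**Step 1. Patients with the longer window.** 200 × infection rate gives 0.4 (0.2%), 1.4 (0.7%), 4 (2%) and 10 (5%).

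**Step 2. Bound.** Protocol 13.4 counts patients per event, so a patient is added to a row only by an event type first seen after Visit 2. If p is the arm's infection rate and q the chance of a new event in the extra window, the added share is p × (1 − b) × q. The artificial difference between arms is (p_control − p_antibiotic) × (1 − b) × q. With q the same in both arms, this cannot exceed p_control − p_antibiotic, and it is zero when the infection rates are equal.

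**Step 3. Constant hazard.** With λ = −ln(1 − b)/t, q = 1 − exp(−λx) = 1 − (1 − b)^(x/t).
- Smallest case (b = 5%, t = 14, x = 7): q = 1 − 0.95^0.5 = 0.0253, so (1 − b)q = 0.0241.
- Largest case (b = 20%, t = 7, x = 28): q = 1 − 0.8^4 = 0.5904, so (1 − b)q = 0.4723.

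Multiplying by the difference in infection rates:

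| Infection rates | Upper bound (points) | Constant hazard (points) |
|---|---|---|
| 0.2% v 0.7% | 0.5 | 0.01 to 0.24 |
| 0.2% v 2% | 1.8 | 0.04 to 0.85 |
| 0.2% v 5% | 4.8 | 0.12 to 2.27 |

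**Step 4. One case in full.** Take b = 10%, t = 7, x = 14 and 0.2% v 5%. Then q = 1 − 0.9² = 0.19 and (1 − b)q = 0.171. Extra patients are 0.4 × 0.171 = 0.07 and 10 × 0.171 = 1.71. The table would show 10.03% v 10.86%, a gap of 0.82 points with no true difference in risk.

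**Step 5. Ratios for a rare event.** Take b = 2% and 0.2% v 5%, with observed rate = b + (1 − b) × p × q.
- If q is simply assumed to be 10% to 50%, control is 2.49% to 4.45%, antibiotic 2.02% to 2.10%, and the ratio 1.23 to 2.12.
- A constant hazard with x/t from 0.5 to 4 gives q = 1 − 0.98^0.5 = 1.0% to 1 − 0.98^4 = 7.8%, and a ratio of only 1.02 to 1.18.
- At 0.2% v 0.7%, even q = 10% to 50% gives only 1.02 to 1.12.

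**Step 6. With a common cut-off at Visit 2.** The extra window contributes nothing to either column, so the window-driven difference is 0 points at any infection rate.

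**The case against.** The strongest reply is that the endpoint that matters is already assessed at a common time. Contact dermatitis and dehiscence are secondary outcomes (SAP 4.2). Protocol 8 and SAP 2 place outcomes at the first post-operative visit, the allergy check is a Visit 2 item for everyone, and the Visit 3 list has no such item. The adverse event table also reports relationship to study drug, so events arising during infection treatment can be graded as unrelated or only possibly related. The SAP plans Fisher's test and a risk ratio for secondary outcomes (6.2) but lists adverse events separately as a safety outcome (4.3), with no test. Onset dates are collected, so the split could be made at reporting.

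Most of this stands. A reader might infer that the design would hide an excess of antibiotic reactions. The documents do not support that, for the reasons just given.

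A reader might also infer that all uninfected patients stop at one visit. The Synopsis allows week 1 and/or week 2, and Protocol 11.1 follows an adverse event that led to withdrawal from treatment until it resolves or stabilises, whatever the infection status. That rule concerns an event already recorded, so it does not equalise the search for new ones.

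The general table is not answered. Relationship is graded by unblinded investigators (Protocol 7.2), and the Possibly grade in Table 2 admits events that other factors could readily explain. SAP 4.3 still points to every clinic visit. A split chosen at reporting is weaker than one stated beforehand.

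**Conclusion.** The point holds for the general adverse event table and not for the ointment-reaction endpoint, which is largely protected. The primary endpoint is unaffected. The unequal window is explicit in the text, and its direction, in expectation, is towards more recorded events in the arm with more infections.

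The size is small: at most 0.5 points at 0.2% v 0.7% and 4.8 points at 0.2% v 5%, or 0.01 to 0.24 and 0.12 to 2.27 points under the constant hazard. These figures rest on assumed adverse event risks and times to resolution, and on infected patients in both arms having the same chance of a later event. The 5% rate is the SAP's maximum acceptable rate, not an expected one.

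A reader might infer a spurious risk ratio of 1.2 to 2.1. That needs an assumed 10% to 50% chance of a new event at the 5% ceiling, and no figure in the documents supports it.

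If the infection itself is recorded as an adverse event, which Protocol 10.1 does not rule out, the infected patient is already in the any-event count at Visit 2. The longer window then affects only individual event types and event counts. This is a cheap improvement to reporting.

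**What to change.** In Protocol 13.4 and SAP 4.3, state that the by-arm adverse event table counts events with onset from the first application of study ointment through the first post-operative visit (Visit 2). This agrees with Protocol 8 and SAP 2. List events with onset after Visit 2 separately by arm, labelled as arising during infection follow-up. If an uninfected patient has a later event recorded, mark it as such in the same listing. Collection and reporting of adverse events, including serious ones, stay as they are.

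The cost is a sentence of wording and one listing. Start and stop dates and times are already recorded (Protocol 8.1.5), so no new data are needed. The downside is that a late ointment reaction first noted at Visit 3 appears in the listing and not in the main table. It remains visible there by arm.

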### 13.5 Interim Analysis

The DSMC will make determinations for interim analysis during their regular review of study data.

### 13.6 Sample Size and Randomization

200 patients will be randomized to the topical antibiotic group and 200 patients will be randomized to the artificial tear ointment group.

## 14 DATA COLLECTION, RETENTION AND MONITORING

### 14.1 Data Collection Instruments

The Investigator will prepare and maintain adequate and accurate source documents designed to record all observations and other pertinent data for each subject treated with the study drug.

Study personnel at each site will enter data from source documents corresponding to a subject's visit into the protocol-specific electronic Case Report Form (eCRF). Subjects will not be identified by name in the study database or on any study documents to be collected by the Sponsor (or designee), but will be identified by a subject number and initials.

*For eCRFs:* If a correction is required for an eCRF, the time and date stamps track the person entering or updating eCRF data and creates an electronic audit trail.

The Investigator is responsible for all information collected on subjects enrolled in this study. All data collected during the course of this study must be reviewed and verified for completeness and accuracy by the Investigator. A copy of the CRF will remain at the Investigator's site at the completion of the study.

## 14.2 Data Management Procedures

The data will be entered into a validated database. The Data Management group will be responsible for data processing, in accordance with procedural documentation. Database lock will occur once quality assurance procedures have been completed.

All procedures for the handling and analysis of data will be conducted using good computing practices meeting FDA guidelines for the handling and analysis of data for clinical trials.

## 14.3 Data Quality Control and Reporting

After data have been entered into the study database, a system of computerized data validation checks will be implemented and applied to the database on a regular basis. Queries are entered, tracked, and resolved through the EDC system directly. The study database will be updated in accordance with the resolved queries. All changes to the study database will be documented.

## 14.4 Archival of Data

The database is safeguarded against unauthorized access by established security procedures; appropriate backup copies of the database and related software files will be maintained. Databases are backed up by the database administrator in conjunction with any updates or changes to the database.

At critical junctures of the protocol (e.g., production of interim reports and final reports), data for analysis is locked and cleaned per established procedures.

## 14.5 Availability and Retention of Investigational Records

The Investigator must make study data accessible to the monitor, other authorized representatives of the Sponsor (or designee), IRB/IEC, and Regulatory Agency (e.g., FDA) inspectors upon request. A file for each subject must be maintained that includes the signed Informed Consent, HIPAA Authorization and Assent Form and copies of all source documentation related to that subject. The Investigator must ensure the reliability and availability of source documents from which the information on the CRF was derived.

All study documents (patient files, signed informed consent forms, copies of CRFs, Study File Notebook, etc.) must be kept secured for a period of two years following marketing of the investigational product or for two years after centers have been notified that the IND has been discontinued. There may be other circumstances for which the Sponsor is required to maintain study records and, therefore, the Sponsor should be contacted prior to removing study records for any reason.

## 14.6 Monitoring

Monitoring visits will be conducted by representatives of the Sponsor according to the U.S. CFR Title 21 Parts 50, 56, and 312 and ICH Guidelines for GCP (E6). By signing this protocol, the Investigator grants permission to the Sponsor (or

designee), and appropriate regulatory authorities to conduct on-site monitoring and/or auditing of all appropriate study documentation.

#### **14.7 Subject Confidentiality**

In order to maintain subject confidentiality, only subject number and subject initials will identify all study subjects on CRFs and other documentation submitted to the Sponsor. Additional subject confidentiality issues (if applicable) are covered in the Clinical Study Agreement.

### **15 ADMINISTRATIVE, ETHICAL, REGULATORY CONSIDERATIONS**

The study will be conducted according to the Declaration of Helsinki, Protection of Human Volunteers (21 CFR 50), Institutional Review Boards (21 CFR 56), and Obligations of Clinical Investigators (21 CFR 312).

To maintain confidentiality, all laboratory specimens, evaluation forms, reports and other records will be identified by a coded number and initials only. All study records will be kept in a locked file cabinet and code sheets linking a patient's name to a patient identification number will be stored separately in another locked file cabinet. Clinical information will not be released without written permission of the subject, except as necessary for monitoring by the FDA. The Investigator must also comply with all applicable privacy regulations (e.g., Health Insurance Portability and Accountability Act of 1996, EU Data Protection Directive 95/46/EC).

#### **15.1 Protocol Amendments**

Any amendment to the protocol will be written by the Sponsor. Protocol amendments cannot be implemented without prior written IRB/IEC approval except as necessary to eliminate immediate safety hazards to patients. A protocol amendment intended to eliminate an apparent immediate hazard to patients may be implemented immediately, provided the IRBs are notified within five working days.

#### **15.2 Institutional Review Boards and Independent Ethics Committees**

The protocol and consent form will be reviewed and approved by the IRB/IEC of each participating center prior to study initiation. Serious adverse experiences regardless of causality will be reported to the IRB/IEC in accordance with the standard operating procedures and policies of the IRB/IEC, and the Investigator will keep the IRB/IEC informed as to the progress of the study. The Investigator will obtain assurance of IRB/IEC compliance with regulations.

Any documents that the IRB/IEC may need to fulfill its responsibilities (such as protocol, protocol amendments, Investigator's Brochure, consent forms, information concerning patient recruitment, payment or compensation procedures, or other pertinent information) will be submitted to the IRB/IEC. The IRB/IECs written unconditional approval of the study protocol and the informed consent form will be in the possession of the Investigator before the study is initiated. The IRB/IECs unconditional approval statement will be transmitted by the Investigator

to the Sponsor or designee prior to the shipment of study supplies to the site. This approval must refer to the study by exact protocol title and number and should identify the documents reviewed and the date of review.

Protocol and/or informed consent modifications or changes may not be initiated without prior written IRB/IEC approval except when necessary to eliminate immediate hazards to the patients or when the change(s) involves only logistical or administrative aspects of the study. Such modifications will be submitted to the IRB/IEC and written verification that the modification was submitted and subsequently approved should be obtained.

The IRB/IEC must be informed of revisions to other documents originally submitted for review; serious and/or unexpected adverse experiences occurring during the study in accordance with the standard operating procedures and policies of the IRB; new information that may affect adversely the safety of the patients of the conduct of the study; an annual update and/or request for re-approval; and when the study has been completed.

### **15.3 Informed Consent Form**

Informed consent will be obtained in accordance with the Declaration of Helsinki, ICH GCP, US Code of Federal Regulations for Protection of Human Subjects (21 CFR 50.25[a,b], CFR 50.27, and CFR Part 56, Subpart A), the Health Insurance Portability and Accountability Act (HIPAA, if applicable), and local regulations.

The Investigator will prepare the informed consent form, assent and HIPAA authorization and provide the documents to the Sponsor or designee for approval prior to submission to the IRB/IEC. The consent form generated by the Investigator must be acceptable to the Sponsor and be approved by the IRB/IEC. The written consent document will embody the elements of informed consent as described in the International Conference on Harmonisation and will also comply with local regulations. The Investigator will send an IRB/IEC-approved copy of the Informed Consent Form to the Sponsor (or designee) for the study file.

A properly executed, written, informed consent will be obtained from each subject prior to entering the subject into the trial. Information should be given in both oral and written form and subjects (or their legal representatives) must be given ample opportunity to inquire about details of the study. If appropriate and required by the local IRB/IEC, assent from the subject will also be obtained. If a subject is unable to sign the informed consent form (ICF) and the HIPAA authorization, a legal representative may sign for the subject. A copy of the signed consent form (and assent) will be given to the subject or legal representative of the subject and the original will be maintained with the subject's records.

### **15.4 Publications**

The preparation and submittal for publication of manuscripts containing the study results shall be in accordance with a process determined by mutual written agreement among the study Sponsor and participating institutions. The publication or presentation of any study results shall comply with all applicable privacy laws,

including, but not limited to, the Health Insurance Portability and Accountability Act of 1996.

